	ARRC Building			
	University of York			
	[name]			
	Email: [contact]			
Qualitative	[name]			
Researcher	York Trials Unit			
	Department of Health Sciences			
	Faculty of Sciences			
	ARRC Building			
	University of York			
	[name]			
	Email: [contact]	c uk		
Data manager	[name]	C.ur		
Data manager	York Trials Unit			
(software development)				
development)	Department of Health Sciences			
	Faculty of Sciences	_		
	ARRC Building, Lower Ground Floo	OT .		
	University of York			
	[name]			
	Email: [contact]			
	[contact] [contact]	[name]		
Data manager	[name]			
	York Trials Unit			
	Department of Health Sciences			
	Faculty of Sciences			
	ARRC Building, Lower Ground Floor			
	University of York			
	[name]			
	Email: [contact]			
	[contact] [contact]	[name]		
Trial oversight	Trial Steering committee:	Data Monitoring and Ethics		
committees	Chair: [name]	Committee:		
	Clinical Trials Research Unit,			
	ScHARR, The University of	Bristol Trials Centre (CTEU),		
	Sheffield, [name]	Bristol Medical School, University		
	[name]	of Bristol, [name]		
	[contact]	[name]		
	Email: [contact]	[name]		
	Linan. [contact]			
	[contact]			
	Email: [contact]			
	Trial Management Group			
	Chair: [name]			
	Department of Trauma and Orthopaedics, Hull and East Yorkshire			
	NHS Hospitals Trust, Hull Royal Infirmary, [name]			
	[name]			
	Email: [contact]			
	[contact]			

Synopsis

Scientific Title	External frame versus internal locking plate for articular pilon fracture fixation: a multi-centre randomised controlled trial			
Public title	Articular pilon fracture trial (ACTIVE)			
Countries of recruitment	England, Scotland, Wales and Northern Ireland			
Health condition studied	Closed pilon fracture of the tibia, classified AO 43- C			
Interventions	Arm 1: Internal fixation: 'Locking' plate fixation with screws	Arm 2: External frame fixation: Limited open reduction and articular fixation using screws & fine wire fixator		
Key Inclusion and Exclusion Criteria	 INCLUSION CRITERIA: Patients aged 16 years or older; With closed pilon fractures, classified AO 43- C which can be bi-lateral and patients with polytrauma; Where the treating surgeon believes the patient will benefit from surgical fixation. EXCLUSION CRITERIA: Prior failed fixation; Pathologic fracture; Patient is/would be unable to understand instructions for treatment More than 21 days since injury Pre-existing (pre-injury) skin condition which precludes 			
Trial Design	open surgery Parallel randomised controlled trial, with an internal pilot			
Trial Participants	Aged 16 years and older			
Planned Sample Size	334 (or revised target of 250)			
Follow up duration	3, 6, 12 and 24 months			
Planned Trial Period	1 September 2017 to 30 th April 2025 (target date of first enrolment 01/03/2018)			
Outcomes	Primary	Secondary		
	Disability Rating Index (DRI) at 12 months	Olerud-Molander Ankle Score (OMAS); DRI; Health related quality of life (EQ5D-5L); Complications (including non-union); Resource use (e.g. impact on the NHS and productivity).		

Abbreviations

AE	Adverse event	
CEAS	Cost-Effectiveness Acceptability Curves	
CI	Chief Investigator	
CONSORT	Consolidated Standards of Reporting Trials	
CRF	Case Report Form	
CRN	Clinical Research Network	
CTA	Clinical Trials Authorisation	
CTRG	Clinical Trials and Research Governance	
DMEC	Data Monitoring and Ethics Committee	
DRAFFT	UK DRAFFT: a randomised controlled trial of percutaneous fixation with Kirschner wires versus volar locking-plate fixation in the treatment of adult patients with a dorsally displaced fracture of the distal radius	
DRI	Disability Rating Index	
EQ5D-5L	EuroQol 5 Dimension, 5-Level scale	
ExFIX	External Fixation	
FixDT	UK FixDT: Fixation of Distal Tibia fractures	
GCP	Good Clinical Practice	
HRA	Health Research Authority	
IB	Investigators Brochure	
ICF	Informed Consent Form	
ICH	International Conference on Harmonisation	
ICER	Incremental Cost Effectiveness Ratio	
IP	Intellectual Property	
IRAS	Integrated Research Application System	
ITT	Intention To Treat	
OMAS	Olerud and Molander Ankle Score	
MTCs	Major Trauma Centres	
NHS	National Health Service	
NICE	National Institute for Health and Clinical Excellence	
NRES	National Research Ethics Service	
ORIF	Open Reduction and Internal Fixation	
PI	Principal Investigator	
PIC	Participant Identification Centre (for a study)	

PIL	Participant/ Patient Information Leaflet
ProFHER	The ProFHER (PROximal Fracture of the Humerus: Evaluation by Randomisation) trial – a pragmatic multicentre randomised controlled trial evaluating the clinical effectiveness and cost-effectiveness of surgical compared with non-surgical treatment for proximal fracture of the humerus in adults
PSSP	Personal Social Services Perspective
QALY	Quality Adjusted Life Year
RCT	Randomised Controlled Trial
R&D	NHS Trust R&D Department
REC	Research Ethics Committee
SAE	Serious Adverse Event
SAP	Statistical Analysis Plan
SD	Standard Deviation
SDV	Source Data Verification
SOP	Standard Operating Procedure
TMF	Trial Master File
YTU	York Trials Unit

1. Background and rationale

A pilon fracture is a severe ankle joint injury to the weight bearing joint surface of the bottom end of the tibia. It is caused by high energy trauma, typically in men of working age (30s to 40s) as a result of a fall from a height or traffic accident [1, 2]. Although pilon fractures are relatively uncommon, 5-7% of all tibial fractures [3-5], the risk of serious complications and long-term disability is high [2, 6].

The force required to create the fracture can lead to complex fracture configurations and extensive soft tissue damage that challenge repair [7]. This is particularly the case for complete articular fractures (Type C). Here, complications are common, and include deep infection, osteomyelitis (infection of the bone), repeat unplanned surgery including arthrodesis (permanently fixing a joint in one position), and amputation with the resultant impact on quality of life [8]. Complications can result in readmission rates of up to 50% [7, 9, 10]. Posttraumatic arthritis also occurs in a high proportion of patients even with adequate restoration of the joint [11]. Treatment is lengthy and costly. People with this injury have among the worst functional and health outcomes for any skeletal injury and it can have persistent and devastating consequences on patients' health and financial prospects [11-14].

Type C pilon fractures are managed surgically using either external fixation or internal fixation. External fixation uses a fine wire frame and pins. Once the fracture is healed, the external fixation is removed. It is often reserved for the most severe fractures, requires specialised training and is often performed in specialist centres. Internal fixation uses a plate and screws to stabilise the fracture and is performed more widely. Fine wire fixation can have a longer procedure time than internal fixation and once fixed can be very inconvenient to patients. One third of patients with external wires and pins develop infection. Although fine wire fixation is associated with a high superficial infection rate, it may lead to less deep infection, amputation and secondary intervention rate [15].

The current choice of treatment is dependent on the surgeons' training, expertise and preferences for a particular treatment. Reviews of the literature have consistently highlighted the need for high quality research, particularly randomised controlled trials (RCTs), to assess whether internal or external fixation is better for definitive management of these injuries [2, 15, 16].

Recent NICE guidance has identified the need to establish whether internal or external fixation is more clinical and cost effective for treating pilon fractures as a high-priority research recommendation [15]. They highlight this to be of high importance to both patients and to society, due to the high risk of early complications and long-term disability. As a national priority question, this research has the potential to impact on the NHS and future NICE guidance [15]. In addition the Orthopaedic Trauma Society undertook a Delphi exercise among 217 consultant orthopaedic surgeons to identify high-priority research questions in orthopaedic surgery [17]. They ranked the need to establish whether internal fixation or external circular frame fixation produces the best outcomes in pilon fractures as the 4th most important research question. Whilst the top three questions have since been addressed, the one regarding fixation remains unanswered.

It has been suggested that the cost of a single use external ring fixator is £2,500, and the cost of a plate with eight screws for internal fixation is £475, [15] though current costs are likely to be higher. While the external fixator is much more expensive than internal fixation, there may be an increased risk of deep infection with internal fixation, which can add significant costs. Direct costs of readmission for failed treatment are between £18,335 and £30,000 and can take four times longer than successful treatment [18-21]. These estimates do not take into account hospital and infrastructure costs, the wider personal and societal costs of morbidity and loss of earnings for the individual nor long-term health burden. If the lower limb is amputated, the costs of initial hospital care, rehabilitation, ongoing support and lifetime use of prosthetics can exceed £320,000 [22]. The implications of such an injury can also lead to financial hardship for the patient: only 28% of patients return to work within 20 months, and 75% report that the injury caused them financial difficulties [23].

A wide range of treatments have been described in the literature, however the standard treatments employed in the NHS for Type C pilon fractures involve either the use of internal fixation or external fixation devices [8]. There is limited evidence in the literature comparing the relative effectiveness of these treatments and that which exists is of poor quality.

NICE undertook a systematic review to establish whether fine wire external fixation is more clinically and cost effective than internal fixation for pilon fractures [15]. No economic evaluations were identified. Two RCTs and one observational study were identified [24-26]. The findings of the two RCTs indicate that internal fixation compared with external fixation may increase osteomyelitis occurrence. One RCT also showed a clinically significant increase in the number of unplanned surgeries, an increase in incidence of wound breakdown and an

increase in incidence of amputation with internal compared with external fixation. The observational study showed that internal fixation was associated with a clinically important higher health-related quality of life compared with external fixation. The quality of the evidence for all the studies was graded as either very low or low. Sample sizes were also small, between 45-60 pilon fractures, meaning that estimates of effect were very imprecise. NICE recommended that research was needed to determine whether internal or external fixation provided the best clinical and cost-effectiveness outcomes [15].

In order to address the evidence gap we will undertake an RCT and economic evaluation to establish whether internal or external fixation is more clinical and cost effective for the management of Type C pilon fractures. The outcome will directly influence clinical decision-making and health policy by informing national guidance, improve outcomes for patients and reduce the financial burden associated with the injury, as well as reduce NHS and wider social care costs.

The injury's rarity means that the involvement of the maximum numbers of centres possible who treat pilon fractures, a high rate of identification of eligible patients, and achieving a high recruitment rate are critical. We will therefore undertake an internal pilot and qualitative study in order to confirm feasibility of the main trial and ensure that trial processes are optimised before proceeding to the full trial. Given that two intensive surgical interventions are being compared we anticipate a higher recruitment rate than would be expected in a study comparing surgery to a non-surgical alternative. Previous orthopaedic trials comparing two surgical interventions have achieved high recruitment rates of around 70%, for example the DRAFTT trial [27]. However, our PPI work suggests that, although both of the interventions are surgical, patients may have strong preferences for receiving either treatment. Non-participation in a previous surgical trial was found to be associated with a concern about receiving a treatment chosen by chance and having a strong preference for a particular treatment [28]. This has been supported by other studies [29, 30]. Surgeons may also have preferences which may subtly influence how they discuss trial participation with patients [31]. These preference issues are not insurmountable but need to be carefully addressed; hence our integrated qualitative recruitment study.

2. Aims and objectives

2.1. Aim

To investigate the clinical and cost-effectiveness of internal plate fixation versus external fine wire fixation for the management of Type C closed pilon fractures of the distal tibia.

2.2. Objectives

Our objectives are to:

- 1. Undertake a 12 month internal pilot to obtain robust estimates of recruitment and confirm trial feasibility
- 2. Explore barriers and facilitators to recruitment during the pilot phase in order to optimise trial procedures and recruitment rates
- 3. Undertake a parallel group multi-centre randomised controlled trial (RCT) to assess the effectiveness of external fixation versus internal fixation for Type C pilon fractures. The primary outcome is patient function at 12 month follow-up, assessed by the patient-reported outcome measure, the Disability Rating Index
- 4. Undertake an economic evaluation to compare the cost-effectiveness of external fixation compared to internal fixation to determine the most efficient provision of future care and to describe the resource impact on the NHS for the two treatment options

3. Trial design

The proposed study will be a multi-centre, randomised controlled superiority trial with parallel groups. An internal pilot phase, with an associated qualitative study, will assess the assumptions about recruitment and provide guidance on optimising the trial processes. A report will be provided to the funder and subject to approval from the funder (assuming feasibility has been established) we will proceed to the main trial.

4. Methods

4.1. Setting

Patients will be recruited from NHS hospitals.

4.2. Eligibility criteria

We will include all adult patients (16 years or older) with type C fractures who meet the eligibility criteria below.

4.2.1. Inclusion criteria

- Patients aged 16 years or older
- With a closed intraarticular pilon fracture of the distal tibia classified according to AO: AO
 43 Cl, C2 and C3 (complete articular). This includes patients with a bi-lateral pilon fracture and who have polytrauma.
- Where the treating surgeon believes the patient will benefit from surgical fixation

4.2.2. Exclusion criteria

- More than 21 days since injury
- Previous failed fixation
- Pathologic fracture
- Pre-existing (pre-injury) skin condition which precludes open surgery
- Patient is/would be unable to understand instructions for treatment

4.3. Interventions

Eligible and consenting patients will be randomly allocated to either internal fixation or external fixation. Surgeons at each recruitment centre skilled in either or both internal and external fixation will perform the surgery according to the patient's random assignment.

4.3.1. Internal fixation

The 'locking' plate is inserted at the distal end of the tibia and passed under the skin on the surface of the bone. The details of the reduction technique, the surgical approach, the type and position of the plate, the number and configuration of fixed-angle screws and any supplementary device or technique will be left to the discretion of the surgeon. The only stipulation is that fixed -angle screws must be used in at least some of the distal screw holes – this is standard practice with all distal tibia 'locking' plates.

4.3.2. External fixation

A limited minimally invasive open reduction and fixation of articular segment is undertaken. Once the articular segment is stabilized, the circular fixator is applied to the bone. Incision site, number and configuration of screws, number of rings, wires and half pins will depend on the fracture configuration and will be left at the discretion of the surgeon. Occasionally, synthetic / iliac crest bone grafts may be necessary and circular fixator will have to extend across the ankle, which again will be left at the discretion of surgeon.

4.3.3. Routine physiotherapy advice

We will ensure that all patients randomised into the two groups will receive standardised, written physiotherapy advice detailing the exercises they need to perform for rehabilitation following their injury. Patients in both groups will be advised to move their toes, ankle and knee joints fully within the limits of their comfort. Early weight-bearing will be encouraged, but the details of weight-bearing status will be decided by the treating surgeon. In this pragmatic trial, any other rehabilitation input including and beyond written physiotherapy advice (such as formal referral to physiotherapy) will be left to the discretion of the treating clinicians. However, a record of any additional rehabilitation input (type of input and number of additional appointments, such hydrotherapy) together with other required investigations/interventions will be self-reported by trial participants as part of the 3, 6 month, 12 month and 24 month follow ups. In addition, detailed data on physiotherapy will be collected from physiotherapists using a specific CRF at the Major Trauma Centres and a sample of local referring hospitals.

4.4. Outcomes

4.4.1. Primary outcome

The primary outcome is the Disability Rating Index (DRI) at 12 months post-randomisation. The DRI is a validated patient-reported outcome measure questionnaire [32]. It consists of a 12-item

Visual Analogue Scale questionnaire assessing the patients' own rating of their disability specifically related to the lower limb. This data will be collected at baseline, 3, 6, 12 and 24 months follow-up post-randomisation. The DRI has been proven to be a robust, practical clinical and research instrument with good responsiveness and acceptability for assessment of disability caused by impairment in the lower limb. Baseline assessment will ask participants about their functioning *before* their injury and *before* their surgery.

4.4.2. Secondary outcomes

- 1. Olerud and Molander Ankle Score (OMAS): The OMAS is an established validated nine-item, patient-reported outcome measure developed and validated for use in clinical trials assessing symptoms following ankle fracture [35]. It contains nine items: pain, stiffness, swelling, stair climbing, running, jumping, squatting, supports and work/activities of daily living. Item responses are each scored from 0 to 25, with 0 representing the most severe state. The scale scores representing each dimension are produced by summing the responses to each item within that dimension. Raw scale scores are then converted to a metric (0-100; 0=most severe) [35]. The OMAS will be collected once at baseline (patients will be asked to complete it thinking about the week before ankle fracture) and then at 3, 6, 12 and 24 months follow-up.
- 2. *EuroQol 5 Dimensions (5L) Score (EQ5D-5L):* The EQ-5D-5L measures health-related quality of life in terms of 5 dimensions: mobility, ability to self-care, ability to undertake usual activities, pain and discomfort, anxiety and depression. Each dimension has five possible responses (no problems, slightly problems, moderate problems, severe problems and unable or extreme problems). The EQ-5D-5L will be scored according to the User Guide [36]. EQ-5D-5L data will be collected twice at baseline: *i.e.* once to assess patient health related quality of life on the day (after the injury) and once with regard to patient health related quality of life during the week before injury; then once each at 3, 6, 12 and 24 months. At baseline, the EQ-5D-5L will be collected before randomisation by patients who have capacity to consent at that time; or at the earliest opportunity after randomisation, by patients who consent having regained capacity.
- 3. *Complications:* Data on all further surgical procedures and other complications, e.g. deep wound infection (using Centres for Disease Control and Prevention definition), superficial infection, pin site infection (defined using the 'Good, Bad and Ugly' pin site grading system [37]), rehospitalisation, blood clots, wound dehiscence, septic arthritis, secondary interventions for non-union and all other secondary procedures will be

- collected by Research Nurses using CRFs for infections and hospital records at 3, 6, 12 and 24 months.
- 3.1. Non-union, mal-union and secondary arthritis. Non-union will be defined as inability to heal as confirmed on x rays / CT scan or as secondary intervention for failure to heal. Mal-union is defined by a standard measurement based on Dror Paley's technique, undertaken using final radiographs at 12 months. Secondary arthritis in the ankle will be assessed using the Kellgren and Laurence scale [38].
- 3.2. To undertake these assessments we will use routine standard radiographs (anterior-posterior and lateral tibia views, with a focus on the ankle for the latter view) and/or when necessary a CT scan of the tibia, fibula and/or ankle, which will be taken at 12 months after the injury. Assessment of imaging will be undertaken by the treating surgeon at the participating site using a proforma which will then be returned to the coordinating centre.
- 4. **Resource use and work impact:** Data on resource use and work impact will be collected to inform the economic evaluation (e.g. length of hospital stay, rehospitalisation and return to work). This data will be gathered through a brief questionnaire administered to patients at 3, 6, 12 and 24 months and hospital records. Table 1 outlines the schedule of events.
- 5. **Patient preference for treatment:** Data on patient preferences will be collected as part of the patient-completed questionnaire to inform the primary statistical analysis model. Patients will be asked about their preferred treatment; and to state if they have no treatment preference at the baseline and 12 month follow-up questionnaire. At 12 month follow-up patients would be asked to state their preference by imagining if they had the same injury again.
- 6. *Transition question:* To assist interpretation of findings, patients will be asked at the 12-month follow-up time-point whether compared with when they initially sustained the pilon fracture one year previously, how their ankle is currently. This will help us to describe clinically important changes for patients, should we identify a difference between the two treatment groups.
- 7. *Free text comments:* Patients will be given the opportunity to highlight any additional issues relevant to their ankle and its impact on their daily activities at the 3, 6, 12 and 24 month time-points.

In Table I we outline the schedule of events for ACTIVE.

Table 1: ACTIVE Schedule of events

Time-point	Baseline	3 month follow- up	6 month follow-up	12 month follow-up	24 month follow- up
PROMS					
Disability Rating Index	X	X	X	X	X
EQ-5D - 5L	X	X	X	X	X
OMAS	X	X	X	X	X
Patient demographics	X				
Resource use		X	X	X	X
Rehabilitation (type/no. of appointments)		X	X	X	X
Return to work/normal activities		X	X	X	X
Free text comments		X	X	X	X
Patient preference for treatment	X			X	
Transition question (Compared with 1 year ago?)				X	

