6.3. Adverse event management

Adverse events (AE) are defined as any untoward medical occurrence in a clinical trial participant and which do not necessarily have a causal relationship with the treatment. We will only collect adverse event data related to treatment for the original injury, that are 'unexpected' and only up until the 24 month follow up. All AEs will be listed on the appropriate Case Report Form for routine return to York Trials Unit. Serious adverse events are defined as any untoward and unexpected medical occurrence that: 1) Results in death; 2) Is life-threatening; 3) Requires hospitalisation or prolongation of existing inpatients' hospitalisation; 4) Results in persistent or significant disability or incapacity; 5) Is a congenital anomaly or birth defect; 6) Any other important medical condition which, although not included in the above, may require medical or surgical intervention to prevent one of the outcomes listed. A list of expected adverse events that we will not report is given in Table 2. This is because these are well known complications

that will be recorded on other CRFs for the two routine surgical treatments that the specialist clinical care teams will be experienced in managing.

Table 2: Expected adverse events

Wound complications (e.g. delayed healing)
Infection at the surgical site or adjacent joint
Pin site infection requiring procedure, antibiotics or admission
Damage to a nerve or blood vessel
Breakage of orthopaedic hardware
Thromboembolic events
Secondary operations for or to prevent infection, malunion, non-union or
for symptoms related to the metalwork.
Wire breakage and removal / exchange of wire
Partial / complete frame removal
Chronic Regional Pain Syndrome
Amputation
Elective admissions to hospital for the ankle
Abnormal blood results related to an infection

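### Mal-union and secondary arthritis rest on 12-month imaging alone, so ankles corrected, fused or amputated earlier go uncounted, whereas non-union also counts earlier intervention

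*Protocol*

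**What the plan says.** Protocol section 4.4.2, item 3.1, defines three related complications.

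- **Non-union:** "Non-union will be defined as inability to heal as confirmed on x rays / CT scan or as secondary intervention for failure to heal". Either the image or an earlier intervention makes a case.
- **Mal-union:** a standard alignment measurement, "undertaken using final radiographs at 12 months". Earlier intervention is not mentioned.
- **Secondary arthritis:** "Secondary arthritis in the ankle will be assessed using the Kellgren and Laurence scale". Earlier intervention is not mentioned here either.

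Item 3.2 says that these assessments use routine radiographs, with CT where necessary, "which will be taken at 12 months after the injury". The treating surgeon at the site reads them on a proforma.

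Item 3 of the same section has research nurses collect all further surgical procedures at 3, 6, 12 and 24 months. Section 5.4.3 analyses binary outcomes of additional procedures and complications by mixed effects logistic regression. No section says how an ankle that was corrected, fused or amputated before the 12-month image is classified for mal-union or arthritis.

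**The concern.** The protocol anticipates the events that remove an ankle from the 12-month reading. Table 2 (section 6.3) lists as expected "Secondary operations for or to prevent infection, malunion, non-union or" metalwork symptoms, and lists amputation separately. Section 1 names among the complications of Type C fractures "repeat unplanned surgery including arthrodesis (permanently fixing a joint in one position), and amputation".

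A mal-union fully corrected at month 6 measures straight at month 12. An ankle fused for arthritis at month 9 has no joint to grade. An amputated limb offers neither reading. Patients whose complication was serious enough to be treated within the year are thus the ones least likely to be counted as having it.

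Two things are at stake. The risks reported for mal-union and arthritis would be too low as statements of how often these complications occur by one year. And if early re-operation is more frequent in one arm, that arm would look better on these two outcomes for that reason alone.

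**Working it through.** **1. The three definitions side by side**

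| Outcome | 12-month imaging | Earlier intervention counts |
|---|---|---|
| Non-union | yes | yes |
| Mal-union | yes | no |
| Secondary arthritis | yes | no |

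The asymmetry lies within one numbered item.

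**2. Is there a figure to reproduce?** No. The protocol states no rate, sample size or power for mal-union or arthritis. The sample size in section 4.5 concerns the DRI only.

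**3. What the rule does to an observed risk.** Let p be the true cumulative risk by 12 months and s the share of affected ankles corrected, fused or amputated before the image.

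- Counted as free of the outcome: observed risk = p(1 − s).
- Dropped as unreadable: observed risk = p(1 − s)/(1 − ps).

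Both are below p whenever s is above zero.

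**4. Illustration with equal true risk.** All rates are assumptions. Take p = 15% in both arms, s = 30% in arm A and 10% in arm B.

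- Counted as free: A = 0.15 × 0.70 = 10.5%; B = 0.15 × 0.90 = 13.5%. Odds ratio = (0.105/0.895)/(0.135/0.865) = 0.75.
- Dropped: A = 0.105/0.955 = 11.0%; B = 0.135/0.985 = 13.7%. The unaffected 85% is the same in both arms, so the odds ratio = 0.105/0.135 = 0.78.

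Varying s in arm A, with arm B held at 10%:

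| s in A v B | Observed A v B (counted as free) | Odds ratio, counted as free | Odds ratio, dropped |
|---|---|---|---|
| 20% v 10% | 12.0% v 13.5% | 0.87 | 0.12/0.135 = 0.89 |
| 30% v 10% | 10.5% v 13.5% | 0.75 | 0.78 |
| 40% v 10% | 9.0% v 13.5% | 0.63 | 0.09/0.135 = 0.67 |

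The true odds ratio is 1 in every row. Exchanging the arms inverts it: the middle row becomes 1/0.75 = 1.33.

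**5. Illustration with early treatment equal in both arms.** Take a true risk of 20% v 10% and s = 25% in both arms. Counted as free, the observed risks are 0.20 × 0.75 = 15.0% and 0.10 × 0.75 = 7.5%. A true difference of 10 points is seen as 7.5. Unequal re-operation is therefore not needed for the absolute difference to shrink.

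**6. Scale in patients.** With the 100 analysed per arm of the revised target (section 4.5), the central case of step 4 is 13.5 − 10.5 = 3 patients.

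**The case against.** The strongest case on the other side has five parts.

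**The events are not lost.** Every further procedure is collected under item 3 and compared under section 5.4.3, so a correction, fusion or amputation still counts against its arm as a procedure. This stands. It limits the harm to the mal-union and arthritis results, but nothing links those procedures to the two definitions.

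**A status at 12 months is a legitimate quantity.** A corrected ankle is not mal-aligned at that time, whereas re-intervention is direct evidence of failure to heal. This has force for mal-union if the aim is alignment at one year. It does not help with a fused or amputated ankle, which has no gradable status, and these outcomes are listed as complications, where a reader expects occurrence.

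**The statistical analysis plan may settle it.** Section 5.4.1 defers full analyses to that plan, which was not available. The coding of unreadable images could be given there. The definitions, however, are stated in the protocol, and a plan that counted earlier intervention would change them.

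**The direction is not established.** A reader might infer a bias in favour of internal fixation, because section 1 reports that "One RCT also showed a clinically significant increase in the number of unplanned surgeries", and more amputation, with internal fixation. The protocol does not support that step. The finding comes from one trial, the evidence is graded low or very low, the studies had 45 to 60 fractures, and nothing is reported by arm on correction of mal-union or fusion for arthritis. Table 2 also lists frame-specific procedures, so re-intervention is not confined to one arm. Its mal-union entry covers preventive operations as well, so it does not show how often established mal-union is corrected.

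**An intervention criterion brings in unblinded judgement.** Section 4.7.1 says that surgeons cannot be blinded. This stands as a cost of the remedy. It already applies to non-union and, because the treating surgeon reads the images, to the imaging criterion too.

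**Conclusion.** The point holds as an undercount of unknown size and direction in two secondary outcomes. As defined, mal-union and secondary arthritis miss ankles whose complication was treated before the 12-month image, and the comparison between arms is distorted if early treatment differs by arm. The odds ratios of 0.63 to 0.89 for a true value of 1 rest wholly on assumed rates (15% risk; 20% to 40% v 10% treated early) and would be inverted if the arms were exchanged. They show that the effect need not be trivial, and they are no estimate for this trial.

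Two limits apply. It would be too strong to say that the worst courses are scored as good or vanish from the trial, because the procedures remain in the complication data and an incompletely corrected mal-union would still be measured as one. The primary DRI analysis and its sample size are untouched. This is an inexpensive improvement worth making to secondary outcomes.

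**What to change.** In section 4.4.2, item 3.1, carry the non-union rule over to the other two outcomes:

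- Mal-union by 12 months: mal-alignment on the 12-month imaging, or a secondary procedure for established mal-union before that image.
- Secondary arthritis by 12 months: the radiographic criterion on the 12-month imaging, or arthrodesis or joint replacement for arthritis before that image.
- Ankles that cannot be read for another reason, such as amputation, are reported as a separate category by arm.
- The imaging-only result is shown as a sensitivity analysis, which also preserves the reading as status at 12 months.

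The procedures are already collected at 3, 6, 12 and 24 months, so no new visit or image is needed. There are two costs. The reason for each procedure has to be coded, with preventive operations kept apart from those for established mal-union, and item 3 does not say that the reason is recorded now. The added criterion also depends on unblinded surgeons' decisions to operate, as the non-union definition already does.
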